An area-based policy could have spillover effects, e.g. if tenants get forced out by increasing rents or a more ardent use of antisocial behaviour clauses. At the same time, landlords and letting agencies could potentially move their businesses away from SL areas to avoid regulation. To study such spillover effects, we have selected areas adjacent to treatment areas. We are acknowledge there are limitations with this definition of spillover – given that displacement of tenants (or landlord properties) may not necessarily be to those adjacent areas. However we have no means of tracking individual displacement events, so our use of adjacent areas represents what we believe to be the best way of assessing this issue that our data will allow. Nonetheless, we will make clear the limitations and clearly designate this part of our analysis as 'secondary.' For simplicity, spillover, and control areas have been defined as mutually exclusive.

Specifically, spillover areas were selected as LSOAs adjacent to treated LSOAs by the year they first gained spillover status. In the selection, treatment status would 'overrule' spillover status. This is particularly evident in London where schemes in some cases are adjacent to other schemes. The exclusion areas, i.e. street-based, 'pre-treated 2007-11', and 'future treated 2020-21' schemes, also

p.17

'overruled' potential spillover status. A small proportion of spillover areas gained that status more than once (N=46, Table 3). This is noted as a limitation but the multiple spillovers will pragmatically be included in the analysis of any spillover effects overall.

A set of spillover control areas will be selected following the same methodology as for the treatment control areas (see next section). All treated units were urban areas and only urban areas were included in the pool of control candidates for treated areas. Since some spillover areas were in fact rural, all areas were included in the pool of candidates for the spillover controls regardless of urbanity.

Selection of control areas

Only areas that were untreated and did not qualify for any of the exclusion criteria were entered into the pool of control candidates (Table 2). SL schemes were only introduced in urban areas and rural LSOA11 were accordingly excluded from the matching pool.

Variables (LSOA11-level) for matching were proportions of the population in receipt of income benefits, self-reported non-white ethnicity, and proportions of households from the private rental sector, living in housing in poor condition, overcrowded, or unaffordable, whether buildings were mainly built before 1945 (Table 4). Skewed variables were logarithmically transformed (natural logarithm) prior to matching.

Propensity score matching (PSM) with 1:3 controls and replacement within each super region was used for the treatment (Table 4, Table S4) and spillover units (Table S5-S6) [29].

Α	В.,	C	D	E
Matching variables	Treated	Never-Treated	Matched Controls	Std. dif. (B-D)
THE NORTH	N=470	N=7,255	N=1,410 (967 unique)	
Age 0-15 years	.18	.19	.18	.06
Age 16-59 years	.63	.58	.64	07
Ln(Income deprivation)	-1.42	-2.04	-1.47	.06
Ln(Private rental)	-1.58	-2.19	-1.57	02
Unaffordability	.93	53	.82	.06
Ln(Poor housing cond.)	-1.34	-1.62	-1.34	<01
Ln(Overcrowding)	-2.56	-3.09	-2.59	.05
Ln(Non-White)	-2.52	-3.18	-2.56	.04
Pre-1945 construction	.76	.45	.76	<.01
THE SOUTH	N=235	N=13,746	N=705 (581 unique)	
Age 0-15 years	.19	.19	.19	11
Age 16-59 years	.66	.58	.65	.10
Ln(Income deprivation)	-1.61	-2.24	-1.57	06
Ln(Private rental)	-1.37	-2.08	-1.42	.08
Unaffordability	1.30	11	1.21	.05
Ln(Poor housing cond.)	-1.26	-1.64	-1.28	.07
Ln(Overcrowding)	-2.10	-2.90	-2.15	.06
Ln(Non-White)	-1.48	-2.73	-1.47	01
Pre-1945 construction	.65	.35	.65	.01

Table 4Baseline characteristics for Treated, Never-treated, and propensity score matched control areas (1 treated:3controls) with replacement. Number of standardised 2011 Lower Layer Super Output Area (LSOA11).

LONDON	N=930	N=3,179	N=2,790 (1,271 unique)	
Age 0-15 years	.22	.19	.22	06
Age 16-59 years	.64	.65	.64	.07
Ln(Income deprivation)	-1.75	-2.12	-1.75	.01
Ln(Private rental)	-1.51	-1.63	-1.58	.11
Unaffordability	2.43	1.55	2.32	.08
Ln(Poor housing cond.)	-1.52	-1.53	-1.53	.03
Ln(Overcrowding)	-1.59	-1.87	-1.65	.08
Ln(Non-White)	72	-1.24	76	.06
Pre-1945 construction	.76	.70	.76	.01

Data sources: Indices of Multiple Deprivation 2015 [30]; Census 2011 [27]. Abbreviation: Households (hh), Standardised distance (Std. dif.). Regions were defined as The North, The South, and London.

Variable transformations

We will apply non-linear DID models [31] such as Poisson models for counts or, alternatively, using logit models and dichotomising the specific outcome variables. This way we can avoid the usual approach of log transforming outcome variables, which has implications for the parallel trend assumption [32]. Log transformation would require as-random treatment allocation (not our case) or checking that the outcome distribution is not affected by the intervention itself. Log transformation also affects the interpretation depending on the model, e.g. from measuring additive to multiplicative effects [33].

Sub-Group Analysis

We will repeat our analyses of individual- and area-level outcomes for the following subgroups:

- Small versus larger SL schemes. We propose this partly because the larger schemes have been politically contentious (following the change of government in 2024, changes were announced to make it easier for LAs to set up large schemes without needing national government permission), and partly because we hypothesise that resident displacement occurs less in larger schemes particularly where the schemes extend across the whole local authority area. For this purpose, we will define larger schemes as those covering 90%+ of the Local Authority population (Census 2011): 2012_Newham, 2014_BarkingandDagenham, 2015_Croydon, 2015_Liverpool, 2015_WalthamForest. Small schemes will in this analysis be defined as those covering up to 20% of the population. Schemes of intermediate sizes will be ignored in this analysis.
- London versus outside London. Comparisons with London are useful because it has a unique housing market and some of its areas were settings for the Olympic Games (a potential confounder).

To examine impacts on equity, we will run the following area-level subgroup analyses by ranking local authorities:

- Level of deprivation: lower half (least deprived), upper half (most deprived)
- **Proportion of population from a Non-White ethnic background**: lower half (low proportion), upper half (high proportion)
- Proportion of population under 16: lower half (low proportion), upper half (high proportion)
- **Proportion of population over 75**: lower half (low proportion), upper half (high proportion)

APS includes items that are relevant to the following equity dimensions covered in the PROGRESS+ framework: Place of residence (which we operationalise as region); Ethnicity, Occupation, Gender, Religion, Education as well as participants who live on their own and participants with child dependents. Occupational status and education can be considered proxies for socio-economic status. Furthermore, the survey asks about long term and limiting health conditions, allowing us to consider these dimensions of disability. It also asks about cohabiting same sex partners. We will incorporate these dimensions into the equity analysis where sample sizes allow us to do so.

To address potential multiple testing issues with the secondary analyses, will adjust the significance tests according to a Benjamini–Hochberg False Discovery Rate of 5% [35].

Software

The analyses will be carried out in Stata (version 18 or later)[36] or R.

19. Handling of missing data

Missing data does not constitute a significant issue with the listed data sources and the analyses will be conducted as complete case only.

20. Handling of withdrawals and replacements

Not applicable.

21. Outcome

Primary and secondary outcomes are described in detail in Section 14.

22. Data confidentiality statement

Quantitative analyses will only involve de-identified secondary data and be carried out on passwordprotected university servers unless otherwise specified by agreements with data providers. Agreements with data providers will be adhered to – including use of secure data environments.

23. Follow-up

The quantitative part of the study will only involve de-identified data where follow-up is not possible.

26. Quality assurance

The quantitative data have been through quality assurance at the source. We will still carry out checks of data completeness, consistency, and outliers. Any changes will be justified and documented in syntax files.

Part D: ETHICAL CONSIDERATION

27. Ethical approval

The project has gone through the ethical approval process at London School of Hygiene & Tropical Medicine (LSHTM submission number: 29809). On obtaining approval from LSHTM, we will then follow ethics requirements for each of the other collaborating universities (Liverpool, Lancaster, Greenwich, Bristol).

The quantitative components of this study are based on routine data analysis so for this part there is no primary data collection. Ethical issues related to this part of the study focus on data privacy and security. We have access agreements with the following data providers: UK Data Service Secure Lab (Annual Population Survey - APS); NHS England / NHS Digital (Hospital Episode Statistics - HES); and Urban Big Data Centre, University of Glasgow (Zoopla data). These will be updated if necessary and adhered to.

We will conduct the quantitative analysis of Annual Population Survey data in ONS's Trusted Research Environment and only be able export results such as regression tables and graphs once these have been subjected to statistical disclosure control checks and cleared for release.

University of Liverpool's HES data sharing agreement (University of Liverpool - data sharing agreement DARS-NIC-16656-D9B5T-v6.1) allows members of the team based at Liverpool access to de-identified and aggregated HES data after a risk assessment within a trusted research environment. The Liverpool team will furthermore ensure that no patient will be indirectly identifiable in the outputs they produce (by e.g., suppressing small numbers or increasing the aggregation level).

Non-personal data from University of Glasgow Urban Big Data Centre (Zoopla property rental price data) will only be stored and handled on collaborating universities' secure servers. The analytical team will ensure that no individual address will be identifiable in the outputs they produce.

The other data we intend to use is publicly available, anonymous and does not pose a risk to individual confidentiality.

28. Consent and assent

The impact evaluation (WP1,3) is based on secondary data analysis with deidentified data and does thus not involve primary data collection.

29. Risk/harm to participants

The impact evaluation (WP1,3) is based on secondary data analysis with deidentified data under secure settings according to data owners' conditions. Residual risks and harms are considered minimal.

30. Adverse and serious adverse event reporting

Not applicable.

Part E: REPORTING AND DISSEMINATION

32. Dissemination/publication plan

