Furthermore, we hypothesise a number of barriers in our proposed pathways to impact (See logic model). For example:

9. NON-COMPLIANCE HYPOTHESIS. Intervention effects may be reduced due to landlord non-compliance at any stage on the pathway to impact (e.g. applying and paying for licenses,

- meeting conditions of licenses, co-operating with the inspection regime, and refurbishing sub-standard properties).
- 10. PARTIAL IMPLEMENTATION HYPOTHESIS. Implementers may lack resource (e.g. finance, workforce) or face other barriers that prevent full implementation.
- 11. LOCAL VARIATION HYPOTHESIS. Local variation in the implementation of SL may lead to local variation in impacts. Local variation can at times be considered positively (e.g. tailoring to local needs) or negatively (e.g. inequities / 'post-code lottery').

WP1 and WP3 include quantitative analyses to identify potentially detrimental effects and (in)equity, while WP2 will use qualitative methods to explore unintended consequences, as well as barriers and facilitators to planned/desired impacts.

We note that we have found it difficult to represent all of these hypotheses diagrammatically in the logic model – we found a mixture of text (ie. above) and diagram easier to work with.

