### Work package 3.

Outcome: Benefit-cost ratio for SL - to monetise the benefits of SL, we will apply the subjective wellbeing approach described in section 18 to the ONS APS outcome: self-reported life satisfaction.

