The four case study sites have been selected to represent different types of SL (smaller and larger) in different regional contexts (north and south). We will use extrapolation methods that use these two broad characteristics as well as cost information obtained through FOI requests to assign costs to the other local authorities that have implemented SL. We will subtract income from license fees, fines and civil penalties to obtain net costs.

In addition, we will estimate the potential costs saved by the NHS through SL's impact on antidepressant prescribing, mental-health related hospital admissions and all-cause hospital admissions over our sample period. If possible, we will also estimate potential cost savings through impacts on mental health-related benefits. If we find substantial cost savings, we will subtract these from the cost of SL to local authorities to obtain net costs from a public sector perspective.

To estimate net costs from a societal perspective we will add back in any income local authorities generate from license fees, fines and civil penalties and try to estimate the costs landlords incur to remove hazards following the receipt of an improvement notice issued by the local authority following an SL inspection.

9b. Study setting

WP1 and WP3 will examine impacts across England.

10. Study schedule

Start date: 1st December 2023

Length: 26 months.

- 0-3 months: ethics approval, PPI & AG meetings
- 2-6 months: WP1 update data, submit protocol
- 7-17 months: WP1 Analysis plan and analysis; WP3 prepare data
- 18-22 months: All WPs: Analysis, interpretive workshops; refine and begin write-up
- 22-26 months: final analysis and write-up.

11. Sample size

Individual-level outcomes

For the individual-level outcome measures, we estimate that the APS includes about 1,000 respondents per year who live in private rented accommodation in LSOAs covered by SL schemes, so over our 2012 to 2019 sample period we expect to observe around 8,000 individuals in the intervention group (5.5% of the England population live in the schemes included in the study). The number of APS participants in the matched comparison LSOAs will be approximately 3000 per year if we match 3 control LSOAs to every intervention LSOA.

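### NHS and benefit-payment effects enter net public-sector cost through an undefined, one-sided rule that depends on the result, with no stated provision for cost increases

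*SAP*

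**What the plan says.** The costing text for work package 3 is in SAP section 9a and protocol section 9a, and is largely repeated in protocol section 18. After deducting licence income from local-authority cost, it adds an NHS component: "we will estimate the potential costs saved by the NHS through SL's impact on antidepressant prescribing", together with admissions for mental health and for any cause. Benefit payments are treated in the same direction: "If possible, we will also estimate potential cost savings through impacts on mental health-related benefits". The rule for using these estimates follows: "If we find substantial cost savings, we will subtract these from the cost of SL to local authorities". The result is called net cost from a public-sector perspective.

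The societal version, in section 9a of both documents, begins: "To estimate net costs from a societal perspective we will add back in any income local authorities generate from license fees, fines and civil penalties". It then adds what landlords spend on removing hazards. It has no term for extra NHS or benefit cost.

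Protocol section 7c states a general intention to look for harm: "WP1 and WP3 include quantitative analyses to identify potentially detrimental effects and (in)equity". Protocol section 21 names the quantity that all this feeds: "Outcome: Benefit-cost ratio for SL".

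**The concern.** The rule has three weaknesses. Inclusion depends on the estimate itself. The threshold word has no amount, percentage or significance level attached. Only the favourable direction is provided for.

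The component is built from estimated impacts on prescribing and admissions, and such estimates can take either sign. The protocol takes unwanted effects seriously: section 7c lists rent rises, lost homes and displacement, and section 7a links insecure tenure to mental wellbeing. It does not say that these raise NHS use, but it gives no ground for assuming that only savings can occur.

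What is at stake is the value-for-money answer. Protocol section 7a says that licence fees may not cover a local authority's full costs, so net cost is what remains after fee income. A component that is deducted or ignored according to its value changes that remainder. SAP Part B says that the plan is settled before any outcome analysis, yet this choice stays open until the results are known.

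**Working it through.** The documents give no NHS cost, no SE and no licensing cost total, so there is no figure of the plan's to reproduce. The check is therefore in units of the SE of the estimated saving.

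**Inputs.** The rule is taken as written in SAP section 9a: deduct the estimated saving S only if it is *substantial*, otherwise deduct nothing. Three things are assumed:
- S is normal with mean μ (the true saving; negative means a true cost increase) and SE 1.
- *Substantial* means S > t.
- t lies between 0 and 1.96. A threshold in pounds corresponds to t = threshold ÷ SE, which may fall outside this range.

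**Formulas.** Expected deduction = μ·[1 − Φ(t − μ)] + φ(t − μ). Bias in net cost = μ − expected deduction. A negative value means that net cost is understated.

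**True effect nil (μ = 0).** The expected deduction reduces to φ(t):
- t = 0: 0.399
- t = 1: 0.242
- t = 1.96: 0.058

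Net cost is understated by these amounts.

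**True cost increase of 1 SE (μ = −1).**
- t = 0: expected deduction = −0.159 + 0.242 = 0.083, so bias = −1 − 0.083 = −1.083.
- t = 1.96: expected deduction is about 0.003, so bias = −1.003.

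**True saving of 1 SE (μ = +1).**
- t = 1: expected deduction = 0.500 + 0.399 = 0.899, so bias = +0.101.
- t = 1.96: expected deduction = 0.169 + 0.252 = 0.420 (from unrounded terms), so bias = +0.580.

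| Threshold t | μ = −1 | μ = 0 | μ = +1 | μ = +2 | True saving at which the sign turns |
|---|---|---|---|---|---|
| 0 | −1.083 | −0.399 | −0.083 | −0.008 | never |
| 0.5 | −1.063 | −0.352 | −0.044 | +0.004 | 1.63 |
| 1 | −1.031 | −0.242 | +0.101 | +0.075 | 0.52 |
| 1.645 | −1.008 | −0.103 | +0.417 | +0.348 | 0.14 |
| 1.96 | −1.003 | −0.058 | +0.580 | +0.569 | 0.07 |

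Simulation with 400,000 draws per cell agreed with the formula to within 0.012 SE.

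**Rule replaced.** If the signed estimate always enters, the expected deduction is μ, and the bias from the inclusion rule is μ − μ = 0 for every true effect.

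**The case against.** A reader might infer that the plan never counts cost increases and that net cost is therefore always biased downward, in favour of licensing. The documents do not support either step.

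First, they are silent on increases; nothing forbids adding them. The stated intention to look for detrimental effects could be read as covering them. That stands as a limit on the claim, but it does not rescue the rule, because no sentence carries an estimated increase into net cost. Nor would adding increases while still filtering savings be neutral. At a nil true effect, net cost would then be overstated by φ(0) − φ(t): 0.399 − 0.242 = 0.157 SE at t = 1, and 0.399 − 0.058 = 0.341 SE at t = 1.96.

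Second, the filter also drops real but modest savings, which counts against licensing. At the stricter thresholds the sign turns at quite small true savings, as the last column of the table shows. A true saving cannot be dismissed: protocol section 7b reports improved scores on the mental health index in the London study, while noting that one scheme drove them.

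Three further points stand. The 0.40 SE figure applies only if any positive estimate counts as *substantial*, which is a generous reading of the word. Reading the threshold in SE units is an assumption. Materiality is not shown, since benefits are valued through life satisfaction and the NHS component is an addition to the cost side.

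It would also be too strong to say that a rise in NHS use would be hidden. The mental health index, its domains and all-cause emergency admissions are outcomes in their own right (section 14a of both documents), so a rise would be reported there. What is unspecified is its entry into net cost.

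**Conclusion.** The concern holds in this form: NHS effects, and benefit-payment effects if estimated, enter net public-sector cost through an undefined, one-sided rule that depends on the result, and no provision is stated for increases. This is more than missing detail, because following the rule as written creates selection bias in net cost and hence in the benefit-cost ratio.

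The direction is not fixed. Net cost is understated when the true effect is nil or a cost increase. It can be overstated when real savings are modest, depending on a threshold that the plan does not give. The sizes in SE units rest on a normal estimate and a threshold between 0 and 1.96 SE. No statement in pounds, or about how far the ratio moves, can be made from the documents.

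**What to change.** In SAP section 9a and protocol sections 9a and 18 (work package 3), replace the conditional sentence with wording such as:

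*The signed estimated change in NHS cost, and in mental health-related benefit payments if estimated, enters net public-sector cost whatever its size, direction or statistical significance. Net cost and the benefit-cost ratio are reported with and without this component, and the uncertainty of the estimate is shown.*

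The preceding sentences should speak of changes in cost rather than savings.

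No new data are needed. The cost is a noisier net-cost figure and a little extra analysis. The work package 3 text describes no interval, so a line is also needed on how the uncertainty will be obtained. The version without the component is close to what the plan already computes after deducting licence income.
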